7.2 Telephone Follow-up (All patients)

All patients who have been randomised to the trial will be followed up by telephone every three months (6/9/12mths) after week 12 visit. Questions asked during this follow-up will cover hospital attendance (reason/outcome/medication changes/investigations), any symptoms experienced and whether the patient needs to see the research team for an unscheduled visit. The Month 12 questions can be done by either telephone or face to face as a part of the End of Study Visit.

7.2.1 Telephone questions;

The staff making the telephone query will be blinded to the treatment arm and may be from a different site. At the beginning of the conversation the caller will explain that they do not know which treatment arm they are in and that they should try to avoid any references to the treatment and just try and answer the question directly. Please see the Appendix 1 for the details of the telephone questions.

7.3 1-Year Follow-up (All patients)

1st Intervention will be considered baseline, all patient returning for follow-up 1 year \pm 14days after this date. At this visit, all patients will undergo the following assessments:

- Physical Examination
- Vital signs
- Concomitant medications
- ECG
- 24 hour holter monitor tape
- EQ5D quality of life questionnaire
- Adverse Events
- Study Endpoints
- Atrial Fibrillation Effect on QualiTy of life (AFEQT) patient questionnaire

All data will be recorded on the InForm eCRF.

8 Endpoints

8.1 Primary Endpoint:

1. Time to any hospital episode (Emergency Room or patient request for OPD) related to treatment for atrial arrhythmia.

8.2 Secondary Endpoints:

1. Time to death or stroke from any cause.
2. Any complications caused by the procedure (pericardial effusion, bleeding >2 units, phrenic nerve palsy and other) or the anti-arrhythmic drug (GI disturbance, skin irritation and other).
3. All hospital episodes which result in a change in therapy for atrial arrhythmia

All study endpoints will be reported from the date of 1st intervention.

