8.3 Crossover between therapies

Following the week 12 visit, a patient from any group, the Investigator may initiate further drug therapy or schedule a standard ablation procedure for the patient. However, the following are required;

- i) *Ablation Arms (Conventional and AVATAR-AF):* Can start anti-arrhythmic drugs or further redo-ablation if there is ECG/Holter documentation of recurrent AF/AT
- ii) *Drug Therapy Arm:* May receive ablation therapy if failed one anti-arrhythmic at maximum standard dose or two anti-arrhythmic agents at sub-maximal dose or due to side effects.
- iii) *New tachycardia documented that needs treatment (VT/AVNRT/AVRT).* The patient is withdrawn from the study

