13.2 Consent

Consent to enter the study must be sought from each participant only after a full explanation has been given, an information sheet offered and time allowed for consideration. Signed participant consent must be obtained. The right of the participant to refuse to participate without giving reasons must be respected. After the participant has entered the study the clinician remains free to give alternative treatment to that specified in the protocol at any stage if he/she feels it is in the participant's best interest, but the reasons for doing so must be recorded. In these cases, the participants remain in the study for the purposes of follow-up and data analysis. All participants are free to withdraw at any time from the protocol treatment without giving reasons and without prejudicing further treatment.

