14.3.2 Early Discontinuation of Individual Subjects

The reason for a patient discontinuing study will be recorded in the case record form. A discontinuation occurs when an enrolled patient permanently and totally withdrew the study consent regardless of the circumstances, prior to completion of the protocol. A discontinuation must be reported immediately to the co-ordinating centre. It may not be necessary for a patient to stop follow-up after an endpoint. The investigator will provide or arrange for appropriate follow-up for such patients, and document the course of the patient's

condition. The patients should, if at all possible, be followed to the end of the study despite reaching the study endpoint as the intention-to-treat analysis includes all patients. Subjects will be informed that they are free to withdraw from the study at any time and for any reason. In case of early discontinuation of a subject, the Follow-up assessments should be performed, as far as possible.

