- g) Did you have any procedures whilst you were in hospital
If yes- what was it

ii) Have you had any of the following symptoms;

- a) racing heart beat lasting more than half an hour
if yes – <1/week or >1/week
- b) racing heart beat more than 5mins but less than half an hour
if yes – <1/week or >1/week
- c) Have you had any unexplained breathlessness, dizzy spells, chest pain, fainting attacks/weakness/confusion
if yes which-

iii) Do you think you the situation is bad enough that you need to change medication or have another procedure to help make you better? (yes/no)

**iv) Do you think you are having side effects or complications from your treatment?
(yes/no)**

v) If you have answered yes to any of the questions we recommend that you see your GP and discuss whether you need another appointment with your heart specialist. We will pass on the information from the phone call to your heart specialist and they may contact you directly if they are concerned about any of the answers you have given.

21 Appendix 2: AVATAR-AF Endpoint definitions

Symptoms of atrial fibrillation/tachycardia:	palpitations lasting >5min, transient dizziness or fainting, lethargy, shortness of breath on exertion, chest discomfort
• ECG documentation:	
• irregularly narrow QRS without p-waves lasting >30secs narrow QRS with A>V evident or 1:1 at >100bpm with sudden onset lasting >30sec or incessant at constant rate
Pericardial Effusion:	global echo-lucent space around myocardium >0.5cm maximally in diastole 
• SEVERE: pericardial drain inserted, sternotomy,• MODERATE: delayed discharge
Vascular Bleeding:	Bleeding visualised by haematoma or imaging associated with Hb drop of >2g/dl 
• SEVERE: Surgical intervention, transfusion required
Phrenic Nerve Palsy:	Reduced excursion of hemi-diaphragm on chest x-ray in inspiration and expiration more than 1day after procedure 
• SEVERE: exertional symptoms with CXR changes at >3mth• MODERATE: asymptomatic with CXR changes at >3mth
PV stenosis:	Evidence of >50 reduction in ostial PV diameter by any form of imaging. 
• SEVERE: exertional symptoms at >3mth• MODERATE: asymptomatic at >3mth
Drug Side Effect:	Symptoms that are well recognised with drug or stop after ceasing drug
Stroke:	logical symptoms/signs associated with MRI or CT evidence of neurological bleeding/ischaemia

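### Protocol 8.3(iii) withdraws patients with new VT, AVNRT or AVRT from the study after week 12, contrary to the protocol's own follow-up and intention-to-treat rules, and the SAP does not say how to handle them

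*Protocol*

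**What the plan says.** Protocol 8.3 governs changes of therapy after the week 12 visit. Items (i) and (ii) allow ablation patients to start drugs or have a further ablation, and drug patients to have an ablation. Neither item withdraws anyone. Item (iii) carries no arm label. Its trigger is "New tachycardia documented that needs treatment (VT/AVNRT/AVRT", with the three rhythms named in brackets, and its consequence is "The patient is withdrawn from the study".

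Other sections that bear on the same patient:

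- Protocol 13.2, where the clinician gives a treatment other than the protocol's: "In these cases, the participants remain in the study for the purposes of follow-up and data analysis".
- Protocol 14.3.2: "A discontinuation occurs when an enrolled patient permanently and totally withdrew the study consent regardless of the circumstances". The same section says that the intention-to-treat analysis covers all patients, and it asks for follow-up assessments where feasible after early discontinuation.
- Protocol 7.2 and 7.3: telephone calls at 6, 9 and 12 months for every randomised patient and a one-year visit for all, with no exception for 8.3(iii).
- Protocol 10.5: adverse events in patients who withdraw early are secured only up to discontinuation, as a minimum.
- Protocol 11.2: intention to treat, but with censoring when a patient switches treatment or leaves the group event-free.
- SAP section 6: an end-of-study visit for patients withdrawn between randomisation and first intervention. Later withdrawals are not mentioned. SAP 8.2 states intention to treat and gives no censoring rule.
- Protocol 8.1, primary endpoint: "Time to any hospital episode (Emergency Room or patient request for OPD) related to treatment for atrial arrhythmia". Protocol 8.2, first secondary endpoint: "Time to death or stroke from any cause".
- Protocol Appendix 2, ECG documentation of atrial fibrillation/tachycardia, includes "narrow QRS with A>V evident or 1:1 at >100bpm with sudden onset lasting >30sec or incessant at constant rate".

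**The concern.** Removal under 8.3(iii) depends on something observed after treatment has started. A ventricular arrhythmia in a patient taking an anti-arrhythmic drug may be an effect of that drug, so the rate of removal could differ between the drug and ablation arms. Censoring such patients as if their departure carried no information is hard to defend, above all for death or stroke, because patients with VT are not a random sample.

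At stake are events after the withdrawal date: deaths, strokes, complications, later hospital episodes, and the month-12 Holter and quality-of-life data. Data that were never collected cannot be recovered at the analysis stage.

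A smaller question concerns adjudication. One hospital visit with a narrow-complex tracing might be put to the committee as atrial arrhythmia under Appendix 2, or treated as the trigger for 8.3(iii). No section says which rule comes first.

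**Working it through.** No figure in the plan quantifies this rule, so the check is mainly a comparison of texts, followed by two illustrations of size.

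**1. Does the patient stay in follow-up?** Take a patient diagnosed with AVNRT that needs treatment at month 5.

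- Protocol 8.3(iii): out of the study.
- Protocol 13.2: if this counts as the clinician giving another treatment, in for follow-up and analysis.
- Protocol 14.3.2: not a discontinuation at all, because consent has not been withdrawn.
- Protocol 7.2 and 7.3: calls at months 6, 9 and 12 and the one-year visit are due.
- Protocol 12: data collection stops on withdrawal of consent, which has not happened.
- Protocol 10.5: adverse events secured only to discontinuation, if the site records one.

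A site can follow 8.3(iii) literally and stop, or follow the other sections and continue. The text does not decide between them.

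**2. How is the patient analysed?** Under Protocol 11.2 the patient could be censored by either limb: leaving the group, or switching treatment if the new therapy counts as a switch. Intention to treat in the same section, and in SAP 8.2, points the other way. SAP section 6 shows that withdrawal was considered, but only before first intervention.

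**3. Can a tracing meet both rules?** The Appendix 2 criterion is narrow QRS, 1:1, above 100 bpm, sudden onset, longer than 30 seconds. An AVNRT or AVRT tracing can meet it, and neither rhythm is excluded. Protocol 8.4 has the committee verify events against the protocol definitions.

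**4. Number of patients.** 321/3 = 107 per arm. The documents give no rate of these tachycardias. Assuming 1–3%: 0.01 × 107 = 1.1 and 0.03 × 107 = 3.2 patients per arm. If every withdrawn patient's primary status changed, the arm's event proportion would move by at most 1–3 percentage points.

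**5. Death or stroke.** No rate is given here either. Assuming 1–2%: 1.1 to 2.1 events per arm. One uncollected event would then be half or all of that arm's total.

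**6. Power for the primary endpoint.** The planned event counts reproduce as 100 × (0.63 + 0.40) = 103 and 100 × (0.40 + 0.20) = 60. The hazard ratios are ln 0.60 / ln 0.37 = 0.514 and ln 0.80 / ln 0.60 = 0.437. Freedman power is Φ(√d × (1 − HR)/(1 + HR) − 2.241) at two-sided alpha 0.025. For the main comparison this gives Φ(10.149 × 0.3212 − 2.241) = 84.6%, above the stated 0.80; that difference does not bear on this point. Now assume a share of patients is withdrawn, all their primary events are lost, and the hazard ratio is unchanged:

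| Share withdrawn | Patients of 321 | AVATAR vs drug: events, power | AVATAR vs conventional: events, power |
|---|---|---|---|
| 0% | 0 | 103.0, 84.6% | 60.0, 78.7% |
| 1% | 3.2 | 102.0, 84.2% | 59.4, 78.2% |
| 2% | 6.4 | 100.9, 83.8% | 58.8, 77.8% |
| 5% | 16.1 | 97.9, 82.5% | 57.0, 76.4% |

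This measures lost precision only. It says nothing about bias from unequal removal between arms, which the documents do not allow one to quantify.

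**The case against.** The strongest reply is that nothing need be lost. A reader of 8.3(iii) might infer that later deaths, strokes and complications are certain to go missing, and the documents do not support that. Protocol 7.2 and 7.3 follow everyone to one year, section 10 collects adverse events from randomisation to the end of the trial, 14.3.2 asks for follow-up assessments even after discontinuation, and 10.5 sets a minimum rather than a limit. This stands: the finding is an unresolved contradiction that puts data at risk.

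Three other stronger readings also fail.

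- A reader might take the rule to cover any new narrow-complex tachycardia. It covers a new tachycardia that needs treatment, names VT, AVNRT and AVRT, and applies after week 12. Recurrent AF or AT falls under 8.3(i), and symptomatic flutter found as an endpoint under item (V) of the flutter guidance in 5.3.
- A reader might take the Appendix 2 rhythm to be an endpoint in itself. It is an ECG documentation criterion. The endpoint is a hospital episode adjudicated from a discharge or clinic letter, and an episode that precedes withdrawal can still count.
- A drug-related VT might seem to vanish from the safety data. The VT itself precedes withdrawal and can be recorded; only what follows it is at risk.

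What the reply does not answer is that 8.3(iii) says study and not treatment, that no section overrides it, and that the SAP has no rule for these patients.

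**Conclusion.** The point holds as a contradiction of moderate importance. Followed literally, 8.3(iii) produces withdrawal that depends on a post-treatment event, against the trial's own intention-to-treat principle, and leaves later safety and month-12 data dependent on how each site reads the protocol.

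Its size is probably small. About 1–3 patients per arm rests on an assumed 1–3%. The effect on primary power is slight: 0.8 points for the main comparison at 2% withdrawn. The primary comparison is therefore not threatened through power.

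The proportionate effect on death or stroke could be larger. That requires an assumed 1–2 events per arm, with one of them falling in a withdrawn patient, after withdrawal, and never being captured. Unequal removal by arm is plausible but unquantified.

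The overlap with Appendix 2 is secondary: the wording is ambiguous for tracings that fit both rules, and precedence is not stated.

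**What to change.** 1. **Protocol 8.3(iii).** State that the diagnosis does not end study follow-up, endpoint collection or inclusion in the intention-to-treat analysis, in any arm. Management of the arrhythmia stays with the clinician and is not part of this request.
2. **Protocol 10.5, 11.2, 13.2 and 14.3.2.** Reconcile them with the revised 8.3(iii). In particular, say that these patients do not count as having left or switched their group for the censoring rule in 11.2, and that adverse events are collected to the end of their follow-up.
3. **SAP sections 6 and 8.2.** State that these patients remain in the intention-to-treat analysis and are not censored at the diagnosis. Report their number by arm.
4. **Appendix 2.** State how the committee adjudicates a tracing that meets the ECG criterion and also falls under 8.3(iii). Setting the precedence is enough.

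The cost is a short protocol amendment and a few sentences in the SAP. No new visits are needed, because the telephone calls and one-year visit are already scheduled for all patients.

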8.4 Endpoint Adjudication

The endpoint adjudication will be done by an independent Endpoint Adjudication Committee (EAC). The EAC will centrally review and classify suspected outcome events, verifying whether they meet protocol definitions. Any hospital episodes (Emergency Room or outpatient) related to treatment for atrial arrhythmia, Stroke or Death from any cause, Any complications caused by the procedure (pericardial effusion, bleeding >2 units, phrenic nerve palsy and other) or the anti-arrhythmic drug (GI disturbance, skin irritation and other), All hospital episodes which result in a change in therapy for atrial arrhythmia.

Any attendance to hospital or specialist cardiac clinic will require the documentation of a discharge letter or clinic letter for primary endpoint adjudication.

Definitions of study endpoints: see Appendix 2

9 Patient visit schedule

PROCEDURE	VISIT (Month)					
	SCREENING (M-0.5 \pm 14d)	1 ST INTERVENTION (M0 \pm 7d)	WK4 REVIEW (M1 \pm 7d)	WK8 REVIEW (M2 \pm 7d)	WK12 REVIEW (M3 \pm 14d)	EOS (M12 \pm 14d)
Obtain Informed Consent	X					
Eligibility Criteria	X					
Vital Signs	X				X	X
Physical Examination	X				X	X
Medical History Assessment	X				X	X
Concomitant Medications	X				X	X
Fasting Blood Sample	X					
Quality of Life Questionnaire	X					X
Allocate 1 ST Intervention date	X					
Randomisation *	X					
Initiate 1 ST Intervention		X				
Allocate possible ablation 're-do' date ** [†]		X				
Review anti-arrhythmic medication			X	X		
Post-ablation symptoms review ** [†]				X	X	
Enter Discharge Protocol					X	
Electrocardiogram						X
24-Hour Holter monitor tape						X
Echocardiogram	X					
Adverse Events		X	X	X	X	X
Study Endpoints			X	X	X	X
AFEQT patient questionnaire	X					X

* = Randomisation date to be scheduled 28d \pm 7d from allocation of 1ST Intervention date

** = AVATAR-protocol ablation arm patients only

† = Anti-arrhythmic therapy arm patients only

^ = Conventional ablation arm patients

10 Safety Reporting

Information about trial adverse events will be collected from randomisation until the end of the trial

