5.4 Randomisation Procedures

Eligible patients who have given written, informed consent and who meet all the inclusion criteria and no exclusion criteria will undergo 1:1:1 randomisation to an un-blinded treatment of either AVATAR-protocol AF Ablation, medical anti-arrhythmic therapy or conventional AF ablation. Randomisation will be performed electronically using the InForm electronic data capture system and will be stratified by site.

From the date of randomisation, the 1st Intervention date (ablation or anti-arrhythmic medication change) must occur 28 days ± 7days after this, therefore an ablation procedure date will be identified according to local EP catheter lab availability for each consenting, eligible patient and randomisation of the patient will then be scheduled for 28 days ± 7days from this available date.

The patient may be withdrawn from any AF ablation treatment by the Investigator if any safety concerns arise during the period between randomisation and the ablation which make the patient an unsuitable candidate for the procedure. The patient will then be withdrawn from the study.

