12 DATA MANAGEMENT AND QUALITY CONTROL

The complete dataset will be collected for all patients who are randomised into the trial. If consent to participate is withdrawn then any data collected will be retained and used in the study, with no further data collected or study procedures carried out on the patient. The electronic data capture system, InForm will be used to document clinical data.

The signed, original informed consent forms and the documentation of all study procedures and assessments will be kept in the patients' study notes. All data to be transferred to the study co-ordination centre with all appropriate supporting documentation will be done as required such as hospital reports or imaging reports with all patient identifiers removed. Patients study documents will be identified by their study-specific patient number allocated at randomisation.

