7.1. Primary Endpoint Variable

Time from 1st intervention to any hospital episodes (Emergency Room or patient request for OPD) related to treatment for atrial arrhythmia that has been formally adjudicated by an independent committee as a primary endpoint. Failure to enter discharge protocol at the Week 12 Review will also result in the primary endpoint being met.

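### Neither document says that the endpoint committee is masked to allocation, although it judges primary events in an open-label trial from letters that probably reveal the arm

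*Protocol*

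**What the plan says.** - **Open label.** Under Protocol 5.4, patients "will undergo 1:1:1 randomisation to an un-blinded treatment of either AVATAR-protocol AF Ablation", drug therapy or conventional ablation.
- **Who adjudicates.** Protocol 8.4: "The endpoint adjudication will be done by an independent Endpoint Adjudication Committee (EAC". Its task: "The EAC will centrally review and classify suspected outcome events, verifying whether they meet protocol definitions". SAP 7.1 requires a hospital episode to be "formally adjudicated by an independent committee as a primary endpoint".
- **From what.** Protocol 8.4: "Any attendance to hospital or specialist cardiac clinic will require the documentation of a discharge letter or clinic letter for primary endpoint adjudication".
- **What is removed.** Protocol 12 describes supporting documents going to the co-ordination centre, such as "hospital reports or imaging reports with all patient identifiers removed". Neither document mentions removing arm, procedure or drug.
- **Where blinding is stated.** Protocol 7.2.1: "The staff making the telephone query will be blinded to the treatment arm". Protocol 7.1 says the same of the research nurse or designee who telephones every three months.
- **A second route.** Under Protocol 7.1.1 and SAP 7.1, failing to enter the discharge protocol at Week 12 also meets the primary endpoint. Neither section attaches adjudication to that route.

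**The concern.** Whether an attendance was connected with treating an atrial arrhythmia is a judgement. Appendix 2 of the protocol defines arrhythmia symptoms and ECG criteria, complications, drug side effects and stroke. It defines neither a hospital episode nor that connection. Several of the listed symptoms (lethargy, chest discomfort, breathlessness on exertion) are non-specific. The outpatient component is also worded in two ways: as a visit the patient requests (Protocol 4.1 and 8.1, SAP 7.1) and simply as an outpatient episode (protocol summary, Protocol 8.4).

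Borderline cases are therefore to be expected, and an adjudicator who knows the arm may resolve them differently by arm. The protocol recognises this risk for the telephone callers. It states no matching protection for the people who decide whether an episode counts. Differential decisions would shift event counts in the log-rank and Cox analyses of both AVATAR comparisons in SAP 8.2.

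**Working it through.** **Step 1: the text on masking.**

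| Step | Blinding stated? | Source |
|---|---|---|
| Treatment | No, open label | Protocol 5.4 |
| Three-monthly calls | Yes, though Month 12 may be face to face | Protocol 7.1, 7.2, 7.2.1 |
| Committee review of episodes | Not stated either way | Protocol 8.4, SAP 7.1 |
| Letters and reports | Patient identifiers only | Protocol 12 |
| Week 12 discharge failure | Not stated; no adjudication attached | Protocol 7.1.1, SAP 7.1 |

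Independence from the trial team is a different property from masking to allocation. The first is stated and the second is not.

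**Step 2: will the letters reveal the arm?** The documents do not describe the letters' content, so this is an inference. The letters concern care after an ablation or a drug change, and the crossover rules in Protocol 8.3 turn on ablation and drug history. Disclosure is likely.

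**Step 3: can the committee be masked for everything?** No. Under Protocol 8.4 it also judges complications of the procedure or drug, and episodes that change therapy. Those judgements need the treatment information. Masking is feasible only for the primary classification, and only if that comes first.

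**Step 4: illustration of size.** No plan figure measures this bias. I used the plan's log-rank method (Freedman).

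Inputs from the plan: 100 evaluable patients per arm, two-sided alpha 0.025, and 12-month proportions of 0.63 (drug) and 0.40 (AVATAR). On these, events = 100 × (0.63 + 0.40) = 103, as stated. HR = ln(0.60)/ln(0.37) = 0.514, and the Freedman power is 0.846 against the stated 0.80. That difference is a separate matter and does not affect this point.

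Assumptions, not in the plan:
- There is no true effect, and both arms have the same candidate-event proportion p.
- Every candidate is upheld in one arm, and a fraction u in the other.

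Formulas:
- q = p·u
- HR = ln(1 − q)/ln(1 − p)
- Events E = 100(p + q)
- d = √E·(1 − HR)/(1 + HR)
- Chance of p ≤ 0.025 = Φ(d − 2.241) + Φ(−d − 2.241)

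Example with p = 0.63 and u = 0.90: q = 0.567, HR = 0.842, E = 119.7, d = 0.94, chance = 0.097.

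| Upheld, u | p = 0.63 | p = 0.50 | p = 0.40 |
|---|---|---|---|
| 1.00 | 2.5% | 2.5% | 2.5% |
| 0.95 | 4.2% | 3.5% | 3.1% |
| 0.90 | 9.7% | 6.6% | 5.1% |
| 0.80 | 34.4% | 21.1% | 14.6% |

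If half of all events arose through the Week 12 route with no adjudication (an assumption), rejecting 10% of the remainder corresponds to the 0.95 row, and rejecting 20% to the 0.90 row.

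**The case against.** A reader might infer that the committee is unmasked, decides every primary event, and leaves the endpoint with no protection. The documents do not support any of these:

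- **Unmasked.** Both documents are silent. Masking may be set out in a working document not supplied here.
- **Every event.** Week 12 discharge failures meet the endpoint with no stated adjudication, apparently on the open-label site's review.
- **No protection.** Review is independent, central and made against protocol definitions, and the calls that help find events are blinded.

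The illustration is also open to attack. No rejection rate comes from the documents. All disputed calls are assumed to go one way in one arm; the formula is symmetric, so the same size of bias could run against AVATAR. It removes the patient's event altogether, whereas a patient with one rejected episode could still fail at a later one. These points stand, so the table shows sensitivity and is not an estimate.

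Masking has limits too. It cannot correct an unblinded patient's decision to seek a visit. Heavy redaction could also remove evidence needed to judge whether an episode concerned arrhythmia treatment, hence the qualifier about feasibility in the fix.

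What survives is the gap: a judgement on the primary endpoint, in an open-label trial, from documents likely to disclose the arm, with no masking stated.

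**Conclusion.** The point holds in this form: masking of the committee for the primary endpoint is not specified, and nothing in the plan as written would keep allocation from it. That the letters disclose the arm is an inference, though a strong one. The size and direction of any bias cannot be derived from the documents. Under the assumed one-arm rejection of 5% to 20%, the nominal 2.5% false-positive rate would become about 3% to 34%. Smaller values apply where fewer events pass through the committee.

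This is an inexpensive improvement that should be made, not a defect that invalidates the design. If the committee is already masked, one sentence in each document settles that part. The handling of Week 12 failures would still need stating.

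**What to change.** In Protocol 8.4 and SAP 7.1:

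1. State that the committee classifies primary-endpoint episodes masked to allocation, from letters with the allocated arm, index procedure and study anti-arrhythmic details redacted where feasible.
2. State that this classification is completed for a patient before the committee reviews that patient's complications or changes in therapy. Do not claim masking for those reviews.
3. Have the committee record each time a letter unmasked it, and report the number by arm. Keep those episodes in the primary result: unmasking may differ by arm, so excluding them could itself create bias.
4. State whether Week 12 failures to enter the discharge protocol go through the same masked review. Otherwise masking the committee leaves that route untouched.

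**Cost.** Redaction is needed for every candidate attendance letter, including those later rejected. That is more than the expected first events: 103 in the two primary arms, or 100 × (0.63 + 0.40 + 0.20) = 123 across all three. Protocol 12 describes general document transfer, so removing treatment details is an added task. Some letters will still reveal the arm.
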